8.5.2 Efficacy Analysis Population

Two populations, the MITT and the ME populations, will be used for the analysis of efficacy data in this study. The ME population will serve as the primary population for efficacy analyses in this study.

The MITT population is defined as all enrolled subjects who receive at least one dose of IV study therapy. In this study, this is identical with the ASaT population. The ME population is a subset of the MITT population that excludes subjects due to major deviations from the protocol that may substantially affect the results of the efficacy analyses. Potential deviations that may result in the exclusion of a subject from the ME population include the following:

1. The subject fails to meet the protocol definition of cIAI or cUTI
2. The subject had significant violations of inclusion/exclusion criteria that could impact the efficacy assessment (e.g., receipt of previous or concurrent systemic antibacterial therapy beyond those allowed per protocol)
3. The subject received less than 96 hours of IV study therapy (16 infusions)
4. (cIAI only) The subject's pre-study/post-operative culture from the site of infection fails to grow at least 1 gram-negative enteric(s) and/or anaerobic pathogen(s) commonly isolated in IAI. (Note: Subjects who fail to grow a single gram-negative enteric and/or anaerobic pathogen from the site of infection are excluded from the ME population. That is, subjects with only gram-positive pathogens identified will be excluded, as well as those who do not grow any pathogens.)

(cUTI only) The subject's pre-study urine culture fails to grow at least 1 gram-negative and/or anaerobic, pathogen at sufficient quantity specified in the inclusion criteria (See Section 5.1.2 for details)

The composition of the ME population at each time point of interest will be made prior to the database lock and will be documented in a separate memo.

Details on the approach to handling missing data are provided in Section 8.6.

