8.6.2 Statistical Methods for Efficacy Analyses

Missing values

In the analyses using the ME population, any subject with missing or indeterminate assessments for a specific endpoint (clinical or microbiological response) at any particular visit will be excluded from the assessment of that response at that time point. Exceptions follow:

1. (cIAI only) Subjects with a missing culture in the setting of a favorable clinical response: In such subjects, even in the setting of a missing culture at a particular time point, a favorable microbiological response will be presumed from the clinical response (i.e., "presumptive eradication").
2. Subjects discontinuing IV study therapy due to lack of efficacy (i.e., withdrawals with subsequent non-study antibiotic therapy, subjects requiring therapy beyond 14 days), including death due to index infection:
 - These subjects will be considered to be "failures" with respect to clinical response at the time of discontinuation and all subsequent time points post discontinuation, irrespective of whether the clinical response is listed as "indeterminate".
 - These subjects will be considered to have presumed persistence with respect to microbiological response at the time of discontinuation and all subsequent time points post discontinuation, irrespective of whether the microbiological response is listed as "indeterminate."

In the analyses using the MITT population, missing or indeterminate clinical or microbiological responses will be considered failure.

Proportions of subjects with favorable clinical/microbiological responses

A 95% CI based on the method of Agresti and Coull will be provided for the proportion of subjects with cIAI in the ME population achieving favorable clinical response at the EOT visit. The same analysis will be performed for the proportion of subjects with cUTI in the ME population achieving favorable microbiological response at the EOT visit. The same measures at the TOC visit will also be analyzed in the same manner. Supportive analysis using the MITT population will also be performed.

Table 18 summarizes key efficacy analyses.

Table 18 Analysis Strategy for Key Efficacy Variables

Endpoint/Variable (Description, Time Point)	Primary vs. supportive approach [†]	Statistical Method	Analysis Population	Missing Data Approach
Primary objectives				
Proportion of subjects with cIAI achieving favorable clinical response at the EOT visit	P	Agresti and Coull	ME	Data as observed [‡]

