	S	Agresti and Coull	MITT	Missing = Failure
Proportion of subjects with cUTI achieving favorable microbiological response at the EOT visit	P	Agresti and Coull	ME	Data as observed [§]
	S	Agresti and Coull	MITT	Missing = Failure
Secondary objectives				
Proportion of subjects with cIAI achieving favorable clinical response at the TOC visit	P	Agresti and Coull	ME	Data as observed [‡]
	S	Agresti and Coull	MITT	Missing = Failure
Proportion of subjects with cUTI achieving favorable microbiological response at the TOC visit	P	Agresti and Coull	ME	Data as observed [§]
	S	Agresti and Coull	MITT	Missing = Failure

[†] P = primary, S = supportive

[‡] Subjects discontinuing IV study therapy due to lack of efficacy will be considered failures with respect to their clinical response. In subjects with missing culture in the setting of a favorable clinical response, a favorable microbiological response will be presumed from the clinical response.

[§] Subjects discontinuing IV study therapy due to lack of efficacy will be considered persistence with respect to their microbiological response.

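### Section 8.5.2 item 3 (under 96 hours of therapy) and the lack-of-efficacy rule in Section 8.6.2 are not reconciled, so early failures can leave the primary ME denominator

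*Combined protocol and SAP*

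**What the plan says.** **Membership (Section 8.5.2).** ME is the primary efficacy population. It is the treated population less subjects with major deviations that could materially affect the efficacy results. The list opens with "Potential deviations that may result in the exclusion of a subject from the ME population", and item 3 is "The subject received less than 96 hours of IV study therapy (16 infusions". Item 3 does not distinguish reasons for the short exposure. On timing, "The composition of the ME population at each time point of interest will be made prior to the database lock", with the result recorded in a memo.

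**Response in ME (Section 8.6.2, missing values).** The lead-in is "In the analyses using the ME population, any subject with missing or indeterminate assessments for a specific endpoint"; such subjects are left out of that assessment, with two exceptions. Exception 2 begins "Subjects discontinuing IV study therapy due to lack of efficacy (i.e., withdrawals with subsequent non-study antibiotic therapy" and also covers subjects who need more than 14 days of therapy and death due to the index infection. These subjects are clinical failures and presumed microbiological persistence from discontinuation onward. No minimum exposure is given.

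**Table 18 footnotes on the primary ME rows.** For cIAI: "Subjects discontinuing IV study therapy due to lack of efficacy will be considered failures with respect to their clinical response". For cUTI: "Subjects discontinuing IV study therapy due to lack of efficacy will be considered persistence with respect to their microbiological response".

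**Supportive analysis.** MITT is every subject who received at least one dose, and "In the analyses using the MITT population, missing or indeterminate clinical or microbiological responses will be considered failure".

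**The concern.** Sections 8.5.2 and 8.6.2 can be read in sequence: the first decides who is in ME, the second assigns responses to those who are. On that reading the lack-of-efficacy rule does not protect a subject who failed before 96 hours, because item 3 can remove the subject before the rule is reached. The rule modifies the handling of missing and indeterminate data; it does not say that it restores membership.

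Such subjects are foreseeable. Section 5.8.1 names the need for other antibacterial therapy as a reason to stop treatment, with no minimum time. The endpoint definitions also give them an outcome. Footnote c of Tables 4 and 6 presumes persistence after a stop for clinical failure even without a culture, and the fallback EOT culture needs only 48 hours of therapy. A cUTI subject who fails between 48 and 96 hours can thus have a defined unfavourable primary outcome and still be open to exclusion.

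Estimating the two response proportions is a primary objective (Section 3.1), so the ME estimate is the main efficacy result. Any error from this source runs in one direction.

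**Working it through.** **Inputs.** The planning example is 40 enrolled, 28 in ME and evaluable, 26 responders (Section 8.9). The interval method is Agresti-Coull at 95% (Section 8.6.2). The number of lack-of-efficacy stops before 96 hours, k, is not in the documents. I assume k = 0 or 1 per cohort, each meeting every other ME criterion.

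**Formula.** ñ = n + z²; p̃ = (x + z²/2)/ñ; limits p̃ ± z√[p̃(1 − p̃)/ñ]; z = 1.96; upper limit cut at 100%.

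**Step 1: reproduce the plan's figure.** For 26/28, ñ = 28 + 3.84 = 31.84 and p̃ = 27.92/31.84 = 0.877. The half-width is 1.96 × √(0.877 × 0.123/31.84) = 0.114. The result is 92.9% (76.3, 99.1), as stated. All eight rows of Table 19 reproduce.

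**Step 2: direction.** Keeping k failures changes x/n to x/(n + k), which is never larger. For k = 1 the fall is x/[n(n + 1)]; here 26/(28 × 29) = 0.032.

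**Step 3: size.** For 26/29, ñ = 32.84 and p̃ = 27.92/32.84 = 0.850, with half-width 0.122. The result is 89.7% (72.8, 97.2). With k = 0 nothing changes. One such subject in each row of Table 19 gives:

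| As planned, % (95% CI) | One early failure kept, % (95% CI) | Fall in estimate (points) | Fall in lower limit (points) |
|---|---|---|---|
| 19/21: 90.5 (69.9, 98.6) | 19/22: 86.4 (65.8, 96.1) | 4.1 | 4.1 |
| 20/21: 95.2 (75.6, 100.0) | 20/22: 90.9 (71.0, 98.7) | 4.3 | 4.6 |
| 25/28: 89.3 (72.0, 97.1) | 25/29: 86.2 (68.8, 95.1) | 3.1 | 3.2 |
| 26/28: 92.9 (76.3, 99.1) | 26/29: 89.7 (72.8, 97.2) | 3.2 | 3.5 |
| 27/28: 96.4 (80.8, 100.0) | 27/29: 93.1 (77.0, 99.2) | 3.3 | 3.8 |
| 32/35: 91.4 (76.9, 97.8) | 32/36: 88.9 (74.1, 96.2) | 2.5 | 2.8 |
| 33/35: 94.3 (80.4, 99.4) | 33/36: 91.7 (77.4, 97.9) | 2.6 | 3.0 |
| 34/35: 97.1 (84.2, 100.0) | 34/36: 94.4 (80.9, 99.4) | 2.7 | 3.3 |

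**Step 4: context.** Phase II ME non-response of any kind at the 250 mg dose (Section 4.1.2) was (81 − 78)/81 = 3.7% in cIAI and (67 − 64)/67 = 4.5% in cUTI. Per 28 subjects that is 28 × 3/81 = 1.0 and 28 × 3/67 = 1.3. The Phase II ME definition is not shown, so these rates do not tell us k.

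**The case against.** **The text can be read to keep these subjects.** Section 8.5.2 excludes for major deviations, and its list is permissive. A stop for lack of efficacy that Section 5.8.1 foresees is not clearly a deviation. Read with exception 2, which is written for ME analyses, a natural result is that the subject stays and counts as a failure. This stands as a possible reading and makes the point one of ambiguity. It is not secured, because item 3 lists short exposure as a potential deviation whatever the reason.

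**Section 8.6.2 does give a rule.** A reader might infer that the plan is silent on early lack-of-efficacy stops. It is not; only the order of precedence against item 3 is missing.

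**The memo may apply a uniform rule.** A reader might infer that membership will be decided subject by subject with outcomes in view. The documents say only that it is settled before lock and documented. Section 8.2 speaks of knowing treatment, not outcomes. In an open-label trial with investigator ratings, knowledge of outcomes is plausible, but it is an inference.

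**A minimum exposure is an ordinary choice for an evaluable population,** and item 3 applies to successes and failures alike. That is fair. The difficulty is narrower: Section 8.6.2 already treats lack-of-efficacy stops as informative.

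**The size is uncertain and the consequence limited.** k may be zero. Adding one failure to an example that already has two gives 3/29 = 10.3% non-response, above both Phase II rates. A shift of 3.2 points lies well inside the plan's interval, which is 99.1 − 76.3 = 22.8 points wide. MITT is prespecified for all four key endpoints and counts these subjects. All of this stands. But MITT can differ from ME by about 40 − 28 = 12 subjects per cohort for every exclusion reason, and it counts missing data as failure, so it cannot isolate this effect or correct the ME figure.

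**Conclusion.** The point holds as an unresolved conflict between two rules. For a lack-of-efficacy stop before 96 hours, the plan does not say whether item 3 or exception 2 prevails. If item 3 prevails, the primary ME rate can only rise. On the assumption of 0 or 1 such subject per cohort, the planning estimate is overstated by 0 or 3.2 points and its lower limit by 0 or 3.5; across Table 19, one subject is worth 2.5 to 4.3 points and 2.8 to 4.6 points.

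Two stronger conclusions are not supported. A reader might infer that the plan requires early failures to be dropped; the permissive wording does not. A reader might also take the Phase II rates as evidence that a whole expected failure will be lost; with the definition not shown and k unknown, they are context only.

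No efficacy hypothesis or success threshold is stated, so the effect is on the reported estimate and not on a prespecified decision. It should be fixed: the gap touches both primary efficacy estimates, its direction is known, and it is cheap to close. Confidence is high for the textual gap, not for any particular size.

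**What to change.** Add a clause to Section 8.5.2 item 3. It should say that the 96-hour criterion does not remove a subject who discontinued IV study therapy for lack of efficacy as Section 8.6.2 defines it (including death due to the index infection) and who meets the other ME criteria. It should also say that such a subject counts as failure or presumed persistence. Report, by cohort, the number of subjects excluded under item 3, with reasons. Section 8.6.3 already displays the primary reason for discontinuation but does not promise a split at 96 hours or by cohort. Section 8.0 allows a change before lock to be documented in the supplemental SAP. Only the analysis population changes; no treatment rule is affected.

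The cost is one clause and one line in the disposition table, with no new data. The ME rate may be slightly less favourable. The clause also introduces an asymmetry: a failure after very short exposure counts, while a short-treated responder may still be excluded. The count by cohort with reasons would show how much this matters.

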8.6 Statistical Methods

This section describes the statistical methods that address the primary and secondary objectives. Methods related to exploratory objectives will be described in the sSAP.

8.6.1 Statistical Methods for Safety Analyses

Safety and tolerability will be assessed by clinical review of all relevant parameters including AEs, vital signs and laboratory tests.

The broad clinical and laboratory AE categories such as any AE, a drug-related AE, a serious AE, an AE which is both drug related and serious, who discontinued IV study therapy due to an AE, and who discontinued IV study therapy due to a drug-related AE, as well as specific AEs (system organ classes and preferred terms) and PDLCs will be summarized by numbers and percentages of subjects, along with 95% CIs based on the method of Agresti and Coull for the proportion of subjects (broad clinical and laboratory AE categories only).

Summary statistics for baseline, on-treatment, and change from baseline values will be provided for continuous measures such as vital signs and laboratory tests.

8.6.2 Statistical Methods for Efficacy Analyses

Missing values

In the analyses using the ME population, any subject with missing or indeterminate assessments for a specific endpoint (clinical or microbiological response) at any particular visit will be excluded from the assessment of that response at that time point. Exceptions follow:

1. (cIAI only) Subjects with a missing culture in the setting of a favorable clinical response: In such subjects, even in the setting of a missing culture at a particular time point, a favorable microbiological response will be presumed from the clinical response (i.e., "presumptive eradication").
2. Subjects discontinuing IV study therapy due to lack of efficacy (i.e., withdrawals with subsequent non-study antibiotic therapy, subjects requiring therapy beyond 14 days), including death due to index infection:
 - These subjects will be considered to be "failures" with respect to clinical response at the time of discontinuation and all subsequent time points post discontinuation, irrespective of whether the clinical response is listed as "indeterminate".
 - These subjects will be considered to have presumed persistence with respect to microbiological response at the time of discontinuation and all subsequent time points post discontinuation, irrespective of whether the microbiological response is listed as "indeterminate."

In the analyses using the MITT population, missing or indeterminate clinical or microbiological responses will be considered failure.

Proportions of subjects with favorable clinical/microbiological responses

A 95% CI based on the method of Agresti and Coull will be provided for the proportion of subjects with cIAI in the ME population achieving favorable clinical response at the EOT visit. The same analysis will be performed for the proportion of subjects with cUTI in the ME population achieving favorable microbiological response at the EOT visit. The same measures at the TOC visit will also be analyzed in the same manner. Supportive analysis using the MITT population will also be performed.

Table 18 summarizes key efficacy analyses.

Table 18 Analysis Strategy for Key Efficacy Variables

Endpoint/Variable (Description, Time Point)	Primary vs. supportive approach [†]	Statistical Method	Analysis Population	Missing Data Approach
Primary objectives				
Proportion of subjects with cIAI achieving favorable clinical response at the EOT visit	P	Agresti and Coull	ME	Data as observed [‡]
	S	Agresti and Coull	MITT	Missing = Failure
Proportion of subjects with cUTI achieving favorable microbiological response at the EOT visit	P	Agresti and Coull	ME	Data as observed [§]
	S	Agresti and Coull	MITT	Missing = Failure
Secondary objectives				
Proportion of subjects with cIAI achieving favorable clinical response at the TOC visit	P	Agresti and Coull	ME	Data as observed [‡]
	S	Agresti and Coull	MITT	Missing = Failure
Proportion of subjects with cUTI achieving favorable microbiological response at the TOC visit	P	Agresti and Coull	ME	Data as observed [§]
	S	Agresti and Coull	MITT	Missing = Failure

[†] P = primary, S = supportive

[‡] Subjects discontinuing IV study therapy due to lack of efficacy will be considered failures with respect to their clinical response. In subjects with missing culture in the setting of a favorable clinical response, a favorable microbiological response will be presumed from the clinical response.

[§] Subjects discontinuing IV study therapy due to lack of efficacy will be considered persistence with respect to their microbiological response.

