Persistence ^c	The follow-up culture at the site of infection taken at the EOT visit (or, if not available, from the last available culture after at least 48 hours of IV study therapy) grows the pathogen found at study entry.
Super infection	The follow-up culture at the site of infection taken at the EOT visit (or, if not available, from the last available culture after at least 48 hours of IV study therapy) grows a pathogen other than a baseline pathogen during the course of IV study therapy OR emergence during IV study therapy of a new pathogen at a distant sterile site along with worsening signs and symptoms of infection.
Indeterminate	
 a) Entry culture at the site of infection either not obtained or no growth; OR b) Follow-up cultures are not available from the site of infection due to subject death or withdrawal from study; OR c) Microbiological data are incomplete; OR d) Assessment not possible due to protocol violation; OR e) Any other circumstance which makes it impossible to define the microbiological response

^a A microbiological response rating will be determined separately for each pathogen isolated at baseline. If a new/emergent pathogen is identified at this visit which was not identified at baseline, the microbiological response rating will be considered “super infection” for any new/emergent pathogen isolated after initiation of IV study therapy.
^b A favorable overall microbiological response at EOT requires “eradication” or “Presumptive eradication” of all baseline pathogens.
^c If a subject is discontinued from IV study therapy due to clinical failure (i.e., unfavorable clinical response), but persistence of the admission pathogen is not confirmed by culture results or no culture is obtained at the time of clinical failure, the admission pathogen will be presumed to have persisted.

Table 5 Definitions of the By-Pathogen Microbiological Response for cIAI at the TOC Visit

Microbiological Response ^{a,b}	Response Definition
Sustained eradication ^c	The follow-up culture at the site of infection taken at TOC visit, shows eradication of the pathogen found at study entry.
Presumptive eradication	Absence of material to culture from the site of infection in a subject who had responded clinically to treatment.

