Persistence	The follow-up culture at the site of infection taken at TOC visit grows the pathogen found at study entry. These subjects are carried forward with this status from the EOT visit otherwise it meets the criteria for 'New infection' or 'Recurrence' to those 2 follow up visit.
New Infection	Eradication of the original pathogen from the site of infection followed by replacement (at the same site and after completion of IV study therapy) by a new species or by a new serotype or biotype of the same organism in the presence of signs or symptoms of infection. If a pathogen was isolated from a site distant to the primary infection after IV study therapy has been completed, then this is also designated as a new infection.
Recurrence	The follow-up culture from the site of infection taken anytime after documented eradication at the EOT visit grows the original pathogen.
Indeterminate	
 a) Follow-up culture is not available at the TOC visit due to subject death or withdrawal from study; OR b) Microbiological data are incomplete; OR c) Assessment not possible due to protocol violation; OR d) Any other circumstance which makes it impossible to define the microbiological response

^a A microbiological response rating will be determined separately for each pathogen isolated at baseline. If a new/emergent pathogen is identified at this visit which was not identified at baseline, the microbiological response rating will be considered a "new infection" for any new/emergent pathogen isolated after initiation of IV study therapy.

^b A favorable overall microbiological response at TOC visit requires "sustained eradication" or "Presumptive eradication" of all baseline pathogens.

^c A microbiological response of "sustained eradication" at TOC is used when the microbiological response assessment at EOT visit is also "eradication".

4.2.3.2.1.2.2 Microbiological Response for cUTI

The following tables are for the definitions of Microbiological Response for cUTI, as described in [Table 6](#) (for the EOT visit) and [Table 7](#) (for the TOC visit).

Table 6 Definitions of the By-Pathogen Microbiological Response Rating for cUTI at the EOT Visit

Microbiological Response ^{a,b}	Response Definition
Eradication	A urine culture taken at the EOT visit ^d shows eradication of the uropathogen (e.g., $\geq 10^5$ CFU/mL is reduced to $< 10^4$ CFU/mL) found at study entry.

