7.1.3.2.2 On-Study Infection-Site Specimens

Infection-site specimens for culture should be obtained according to Section 6.0 (Trial Flow Chart).

For subjects with cIAI, collection of specimens from the infection site is preferred; however, for subjects in which infection site specimen collection is not medically acceptable follow up specimen is not required. Additional unscheduled cultures from the infection site should also be collected at the time of any surgical or drainage procedure (if required).

For subjects with cUTI, infection-site specimens for culture are required for all visits specified in Section 6.0 (Trial Flow Chart).

Culture should be performed at the local microbiology laboratory according to recognized methods and per each laboratory's standard procedures. Relevant culture data from these samples should also be recorded on the appropriate eCRFs. Suspected causative bacterial pathogens should also be stored at the local laboratory for possible future testing. Relevant culture data from these samples should also be recorded on the appropriate eCRFs.

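### Exploratory cIAI microbiological response at TOC: the ME rules presume eradication for uncultured clinical successes but drop uncultured completers who fail clinically, which biases the rate upward

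*Combined protocol and SAP*

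**What the plan says.** Section 8.6.2 sets the default for the ME population: a subject whose assessment is missing or indeterminate "at any particular visit will be excluded from the assessment of that response at that time point". Two exceptions follow.

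- **Exception 1 (cIAI only)** fills in a favorable result: "even in the setting of a missing culture at a particular time point, a favorable microbiological response will be presumed from the clinical response". Footnote ‡ of Table 18 repeats it.
- **Exception 2** presumes persistence, but its trigger is stopping treatment. It covers "Subjects discontinuing IV study therapy due to lack of efficacy (i.e., withdrawals with subsequent non-study antibiotic therapy, subjects requiring therapy beyond 14 days"), together with death from the index infection.

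The rating definitions are in section 4.2.3.2.1.2.1. Footnote c of Table 4, for end of therapy (EOT), also presumes persistence, with the condition "If a subject is discontinued from IV study therapy due to clinical failure (i.e., unfavorable clinical response"). Table 5, for TOC, has no such footnote. It defines presumptive eradication as "Absence of material to culture from the site of infection in a subject who had responded clinically to treatment". It defines persistence as "The follow-up culture at the site of infection taken at TOC visit grows the pathogen found at study entry", and adds "These subjects are carried forward with this status from the EOT visit". Recurrence also needs growth of the original pathogen, after eradication documented at EOT.

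On sampling, section 7.1.3.2.2 states that "for subjects in which infection site specimen collection is not medically acceptable follow up specimen is not required". The same section asks for a culture at any surgical or drainage procedure.

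**The concern.** When the culture is missing, the clinical result is used to fill in the microbiological one. At TOC this works fully in the favorable direction. In the unfavorable direction it reaches only subjects who stopped IV therapy for lack of efficacy, plus persistence already assigned at EOT.

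The path that falls between the rules is an ordinary one. A clinical rating of Improved is favorable at EOT (Table 2). At TOC, improvement that stops short of full resolution is classed as Failure (Table 3). A subject can therefore finish therapy as a success and be a clinical failure at the next visit with no accessible specimen.

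What is at stake is exploratory objective 1 in section 3.3, the cIAI microbiological response. Its ME rate at TOC would lose some clinical failures while keeping every uncultured clinical success. It could then stand well above the clinical cure rate in the same subjects for reasons unrelated to any culture.

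**Working it through.** **Step 1. Place the subject in the tables.** Take a cIAI subject in the ME population who completes IV therapy, is Improved with presumptive eradication at EOT, and is a clinical Failure at TOC without a procedure or a specimen.

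| Rule | Requirement | Met? |
|---|---|---|
| Table 5, Sustained eradication | negative TOC culture | no |
| Table 5, Persistence | growth at TOC, or persistence carried from EOT | no |
| Table 5, Recurrence | growth after documented eradication | no |
| Table 5, New infection | a new pathogen isolated | no |
| 8.6.2, exception 1 | favorable clinical response | no |
| 8.6.2, exception 2 | IV therapy stopped for lack of efficacy | no |
| Table 4, footnote c | discontinued for clinical failure (EOT only) | no |

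What remains is Indeterminate, which 8.6.2 excludes. Presumptive eradication in Table 5 is taken up under the objection.

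**Step 2. Reproduce the plan's interval.** Agresti–Coull with z = 1.96 and z² = 3.84: ñ = n + z², p̃ = (x + z²/2)/ñ, limits p̃ ± z√(p̃(1 − p̃)/ñ), cut off at 100%. For 26/28: ñ = 31.84, p̃ = 27.92/31.84 = 0.877, half-width 0.114, giving 92.9% (76.3, 99.1), as in section 8.9. All eight rows of Table 19 reproduce.

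**Step 3. Size of the shift.** Let n be the ME cIAI subjects, f the completers who are clinical failures at TOC, and m those of the f without a TOC culture.

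- Rule as written: (n − f)/(n − m)
- Failures without culture counted as unfavorable: (n − f)/n
- Shift: (n − f)m / [n(n − m)]

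From the plan: n = 28, which is 70% of 40 (section 8.9, stated for EOT and assumed here to hold at TOC). Assumed, because the documents give no figures: f and m, that all other subjects are favorable, and that cultured failures grow the baseline pathogen.

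| f | m | As written (95% CI) | Counted unfavorable (95% CI) | Shift (points) |
|---|---|---|---|---|
| 4 | 0 | 24/28 = 85.7% (67.9, 94.9) | 24/28 = 85.7% (67.9, 94.9) | 0 |
| 4 | 2 | 24/26 = 92.3% (74.7, 99.0) | 24/28 = 85.7% (67.9, 94.9) | +6.6 |
| 2 | 2 | 26/26 = 100% (84.8, 100) | 26/28 = 92.9% (76.3, 99.1) | +7.1 |
| 4 | 4 | 24/24 = 100% (83.7, 100) | 24/28 = 85.7% (67.9, 94.9) | +14.3 |
| 6 | 6 | 22/22 = 100% (82.5, 100) | 22/28 = 78.6% (60.1, 90.1) | +21.4 |

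Per uncultured failure this is 3.3 points (6.6/2) to 3.6 points (7.1/2, 14.3/4 and 21.4/6).

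**Step 4. Other cases.** With f = m = 4 and one further subject kept as persistence after stopping for lack of efficacy, the rates are 23/24 = 95.8% and 23/28 = 82.1%. With f = m = 4 and the other ME sizes in Table 19, they are 100% against 81.0% (n = 21) and 100% against 88.6% (n = 35).

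**The case against.** **The endpoint is exploratory and its methods are deferred.** Section 8.6 leaves exploratory methods to the supplemental SAP, which is not among the documents and could close the gap. This limits the weight of the point. It does not remove it, because 8.6.2 and Table 18 already fix the favorable half of the rule.

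**The MITT analysis counts these subjects as failures.** It does if they are rated Indeterminate, and the TOC clinical cure rate will be reported beside it. But ME is the primary efficacy population, and Table 18 lists supportive MITT analyses only for primary and secondary endpoints.

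**Clinical failure at TOC is not proof of persistence.** This stands. Failure includes incomplete improvement, so some subjects counted as unfavorable may have cleared the pathogen. The 85.7% above is an alternative imputation, not the true rate.

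**Stronger readings that the documents do not support.**

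- A reader might infer that cIAI follow-up cultures are optional and that most TOC ratings are inferred. The flow chart schedules them at Day 3, EOT and TOC, the waiver applies only where collection is not medically acceptable, and no missing-culture rate is given.
- A reader might infer that the rate is bound to approach 100%. It reaches 100% only if every unfavorable subject is an uncultured completer. Culture-positive failures, persistence carried from EOT, discontinuations for lack of efficacy and deaths from the index infection all stay in as unfavorable.
- A reader might infer that a failing subject would be scored as presumptive eradication because of an earlier response. The past tense in Table 5 leaves room for that, but exception 1 links the presumption to a particular time point. This is loose wording to tidy, not a stated rule.
- A reader might extend the point to EOT. Exception 2 and Table 4 footnote c already capture most failures there.

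**Conclusion.** The point holds for one endpoint: cIAI microbiological response at TOC in the ME population. The rules presume success without a culture but do not presume failure for therapy completers, and the resulting bias can only be upward.

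Its size cannot be read from the documents. With 28 ME subjects it is about 3 to 4 points per uncultured completer failure: none if all failures are cultured, 6.6 points if 2 of 4 are not, and 14.3 points if none of the 4 is. All of these failure counts are assumptions.

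A reader might take this as a weakness in the main efficacy results. It is not: the primary and secondary cIAI endpoints are clinical response, and exception 1 does not apply to cUTI. The change is worth making because the favorable half of the rule is already written and the trial is open-label, so the other half should be fixed before outcomes are reviewed.

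**What to change.** In section 8.6.2 and Table 5, or in the supplemental SAP:

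1. State that a cIAI subject with a clinical response of Failure at TOC and no TOC culture is counted as microbiologically unfavorable in the ME analysis, as presumed persistence or presumptive recurrence, whether or not IV therapy was discontinued.
2. Tie presumptive eradication in Table 5 to a favorable clinical response at the same visit.
3. Report how many ratings are presumed and how many are documented by culture, for favorable and unfavorable results separately.

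Table 4 needs no change. The cost is wording only, with no new data. The rate will be less favorable, and some subjects with incomplete clinical resolution may be counted as unfavorable although the pathogen was eradicated. The split in item 3 makes that visible.
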